University of Kansas Medical Center
RESEARCH PROTOCOL INVOLVING HUMAN SUBJECTS TEMPLATE

Version date: October 1, 2018

Principal Investigator: [name], MS

Study Title: An open-label pilot study of the effect of intra-articular bilateral knee injections of Zilretta on OARSI recommended physical performance measures in adults with symptomatic knee osteoarthritis.

Co-Investigator(s): [name]

I. Purpose, Background, and Rationale

A. Aim and Hypotheses

This study will be an open-label trial to determine the functional effects of bilateral IA injections of Zilretta into knee joints of 70 subjects with bilateral KL grade 2-4 symptomatic knee osteoarthritis (OA). Measurement and evaluation of outcomes at baseline, 6, 12 and 24 weeks will allow assessment of short and long-term effects, consistent with Osteoarthritis Research Society International (OARSI) and Outcome Measures in Rheumatology (OMERACT) recommendations.

The **primary** aim of the proposed study is to demonstrate the effect of IA injection of Zilretta on physical performance measures in adults with bilateral knee OA. We will test this primary study endpoint by assessing the change in OARSI recommended physical performance tests¹ (30-second chair standing test, 40m fast-paced walking test, stair ascent) 6, 12 (primary) and 24 weeks after treatment.

The secondary outcome will be the change in Knee Injury and Osteoarthritis Outcome Score (KOOS-PS) at 6, 12 (main) and 24 weeks after treatment. This will be captured using the patient-reported physical function short form.

The tertiary outcomes will be the change in KOOS-Quality of life subscale (QoL) and Numerical Rating Scale (NRS) for pain. While the primary outcomes will be defined at the 12-week follow-up, all outcomes will be assessed at the 6- and 24-week follow-up as well to define the course and trajectory of effects.

We hypothesize that people with bilateral symptomatic knee OA will experience significant improvement in physical performance, physical function and quality of life for at least 12 weeks following treatment. Based on research done using Zilretta in patients with knee OA, we anticipate that it will have a greater magnitude and duration of analgesic effect along with significantly fewer adverse events when compared to the rates reported for standard of care therapy (i.e. immediate release corticosteroid injection).²

Specific Aim 1: To determine the extent to which intra-articular (IA) injection of Zilretta in patients with bilateral knee OA improves physical performance (OARSI recommended physical performance measures).

Primary Hypothesis 1: Bilateral knee intra-articular injection of Zilretta results in improved physical performance detectable at: a) 6 weeks, b) 12 weeks (primary), and c) 24 weeks.

Specific Aim 2: To determine the extent to which IA injection of Zilretta in patients with bilateral knee OA improves physical function (KOOS-PF).

Hypothesis 2: Bilateral knee IA injection of Zilretta results in improved patient-reported physical function (KOOS-PS) at: a) 6 weeks, b) 12 weeks, and c) 24 weeks.

Specific Aim 3: To determine the extent to which bilateral knee IA injection of Zilretta in patients with bilateral knee OA improves quality of life (KOOS-QoL).

Hypothesis 3: Intra-articular (IA) bilateral knee injection of Zilretta in patients with bilateral knee osteoarthritis results in improved quality of life (KOOS-QoL) detectable at: a) 6 weeks, b) 12 weeks, and c) 24 weeks.

B. Background and Significance

Osteoarthritis (OA) is the most common disabling disease in older adults, affecting over 27 million Americans, resulting in significantly impaired function and mobility and a societal economic burden. OA is a joint disorder characterized by structural pathology that involves the whole joint, including cartilage lesions, bone remodeling, osteophyte formation, and joint inflammation, among others, leading to symptoms and loss of normal joint function. OA typically becomes symptomatic later in life, usually after age 50, though it may start earlier, such as when a joint injury has occurred or in familial forms. It is the most common form of arthritis worldwide, affecting an estimated 250 million people; about 80% of people over 65 having radiographic evidence of OA.

OA is a leading cause of disability among elderly in the US. In recent estimates of global years lived with disability, musculoskeletal-related conditions ranked second, with low back pain, neck pain, and knee OA being the three most common conditions³. There is a high prevalence of knee OA globally⁴ and it ranked within the top 10 causes of disability and non-communicable diseases for global disability-adjusted life years worldwide (*i.e.*, years of life lost and years lived with disability)^{3,5}. The public health impact of OA is significant on both individuals and society due to the absence of a cure, making symptomatic treatment essential.

The greatest challenge, affecting patients with OA of the hips and knees, is pain and stiffness in these joints, which often leads to significant disability requiring surgical intervention. In a longitudinal panel survey conducted by the US Census Bureau, arthritis or rheumatism was the most commonly reported cause of disability, and difficulties related to lower extremity functioning or activities were the most commonly reported limitations among all respondents. In particular, the most widely recognized limitation was in walking 3 city blocks, which influenced an estimated 22.5 million US adults, and difficulty with climbing stairs, influencing an estimated 21.7 million US adults⁶.

Zilretta is an extended-release PLGA microsphere preparation of triamcinolone acetonide which is FDA approved for treatment of knee pain due to osteoarthritis. Zilretta (triamcinolone acetonide extended-release) is formulated using proprietary microsphere technology combining triamcinolone acetonide with a polylactic-co-glycolic acid (PLGA) matrix. Zilretta received Fast Track Designation from the FDA. This designation is reserved for drugs in clinical development that is intended to treat a serious condition and addresses an unmet medical need.

Preliminary Data: In previous clinical trials, Zilretta (triamcinolone acetonide extended-release) provided an extended and predictable release of triamcinolone acetonide as the biocompatible PLGA microspheres slowly degraded. A single IA dose of Zilretta resulted in less systemically bioavailable triamcinolone acetonide when compared to a matched dose of triamcinolone acetonide crystalline suspension (TAcS)⁷ due to slower release and absorption into the systemic circulation. By providing prolonged local exposure to triamcinolone acetonide while minimizing systemic exposure, IA injection of Zilretta is expected to have sustained anti-inflammatory and analgesic efficacy while minimizing adverse effects⁸. A prior clinical trial provided evidence for analgesic efficacy for knee OA, with a significant reduction in average daily pain (ADP) sustained through 12-week follow-up⁹.

Therefore, the **primary** aim of the proposed study is to demonstrate the effects of IA injection of Zilretta on physical performance in adults with bilateral knee OA. We propose to determine the change in OARSI recommended¹⁰ physical performance measures (30-second chair stand time, 40m fast-paced walking time, stair ascent time) along with patient-reported physical function (KOOS-PS) and quality of life (KOOS-QoL) at baseline and at intervals following bilateral knee injection of Zilretta. The expected deliverables of this research will be evidence regarding the effects of Zilretta on objective and patient-reported physical functional outcomes in patients with bilateral symptomatic knee OA.

C. Rationale

Disability due to knee OA is based on the inter-relationships of pathology (e.g. knee cartilage degeneration), impairments (e.g. pain), functional limitations (e.g. difficulties with standing from a chair, walking or using stairs), and disability (e.g. inability to participate in community). Biomedical research frequently focuses primarily on pathology and sometimes on impairments. However, there is an imperfect correlation between impairments and functional limitations. While the effect of Zilretta on pain has been explored, the effects on physical function and performance are incompletely understood.

II. Research Plan and Design

A. Study Objectives: The goal of this study is to evaluate the efficacy of Zilretta for improving physical performance, physical function, and quality of life.

B. Study Type and Design:

This will be an open-label study to determine the functional effects of IA injection of Zilretta into bilateral knees of 70 subjects with KL grade 2-4 symptomatic knee OA. Measurement of OARSI recommended physical performance measures¹⁰, patient-reported physical function, quality of life and pain at baseline, 6, 12 and 24 weeks will allow assessment of short and long-term effects, consistent with OARSI and OMERACT recommendations. Adverse events will be monitored.

Each subject will participate for up to 24 weeks following the intra-articular Zilretta injection. Enrollment is expected to take approximately 6 months. Total study duration is expected to require at least 12 months.

C. Sample size, statistical methods, and power calculation

In this open-label study, all subjects will receive a single IA Zilretta injection into each knee. Outcome measures will be collected at baseline, 6, 12 (primary) and 24 weeks post-treatment. A 24-week follow-up duration was selected to detect meaningful differences from standard of care (IA corticosteroids - TAcS) and long-term effects, while minimizing the variability that may occur further out from treatment. The overall type I error rate will be controlled with an alpha level of 0.0167 to account for three comparisons at the primary time point.

Based on the respective MDC₉₅ calculated from the standard error of the mean change for OARSI recommended physical performance¹, the effect size for this minimal detectable change is 0.392. To detect an effect size at least this large, with an adjusted alpha of 0.0167 and 80% power, a sample size of 60 would be required. To accommodate up to 14% dropout, we plan to recruit 70 subjects.

D. Subject Criteria (See Vulnerable Populations appendix, if applicable):

Enrollment will be comprised of 70 subjects age 30 and over with symptomatic bilateral knee OA. There will be no exclusions based on sex or ethnic group. Potential subjects will be identified through hospital records, referrals from physicians in the surrounding community, mass mailings, and advertisements posted in area clinics and businesses. Any study-related advertisements will be approved by the IRB prior to use. Subjects will be recruited based upon inclusion and exclusion criteria detailed below.

1. Inclusion Criteria

- Men and women age 30 years or older with symptomatic bilateral knee OA.
- Symptomatic Knee OA will be defined as the presence of a definite osteophyte or joint space narrowing (KL Grade ≥ 2) on posteroanterior (PA) fixed flexion knee radiographs in subjects limited by bilateral pain in each knee, rated on a Numerical Rating Scale as $\geq 4/10$ on more than half of the days over the past month. Radiographic change must be visible at standard image size, irrespective of capability to detect more subtle changes through digital enhancement.
- Bilateral knee symptoms for ≥ 3 months prior to screening.
- Undergone at least one prior conservative osteoarthritis treatment (e.g. physical therapy, analgesics).
- Body Mass Index ≤ 40 kg/m².
- Ambulatory.
- Willing and able to comply with the study procedures and visit schedules and ability to follow verbal and written instructions.
- Willing to abstain from the use of protocol-restricted medications during the study after signing Informed Consent (Refer to §II.5) and also willing to abstain from use of all analgesics other than acetaminophen 1 week prior to the beginning of treatment.

2. Exclusion Criteria

- Current consumption of more than 14 alcoholic drinks per week.
- Clinical signs and symptoms of active knee infection or crystal disease of either knee within 1 month of screening.
- Diagnosed with rheumatoid arthritis, Reiter's syndrome, psoriatic arthritis, gout, ankylosing spondylitis, or arthritis secondary to other inflammatory diseases; HIV, viral hepatitis; chondrocalcinosis, Paget's disease, or villonodular synovitis.
- Diagnosed with leukemia, known presence of metastatic malignant cells, or ongoing or planned chemotherapeutic treatment.
- Diseases of the spine, hip or other lower extremity joints judged by the investigator to be contributing to the pain in either knee (i.e. sciatica, nerve pain, hip OA). Note: Patients with hip replacement in either hip may be enrolled provided there is sufficient pain relief after hip replacement that analgesics are not required
- Untreated symptomatic injury of either knee (e.g., acute traumatic injury, anterior cruciate ligament injury, clinically symptomatic meniscus injury characterized by a mechanical issue such as locking or catching).
- Uncontrolled diabetes.
- Women who report pregnancy or childbearing potential and not using acceptable contraceptive measures (oral contraceptive, long acting reversible contraceptive therapy) (due to the potential for change in body mass and distribution to alter knee symptoms over the period of follow-up).
- Presence of surgical hardware or other foreign body intended to treat arthritis or cartilage-related pathology in either knee.
- Arthroscopy or open surgery of either knee within 6 months of screening.
- Planned/anticipated surgery of either knee during the study period.
- Use of systemic immunosuppressant within 6 weeks of screening.
- Oral corticosteroids (investigational or marketed) within 2 weeks of screening.
- IA corticosteroid (investigational or marketed) in either knee within 3 months of screening.
- IV or IM corticosteroid (investigational or marketed) within 3 months of screening.
- Any other IA drug/biologic use within 6 months of screening or 5 half-lives (whichever is longer) (e.g., hyaluronic acid, platelet-rich plasma (PRP) injection, stem cells, prolotherapy and amniotic fluid injection).
- Any documented clinically significant degree of cognitive impairment or other condition, finding, or psychiatric illness at screening which, in the opinion of the investigator, could compromise subject safety.
- Any condition other than OA of the knee which, in the opinion of the investigator, affects the ability to ambulate to a sufficient degree to interfere with the assessment of the safety and treatment effects of the study injection.
- Participated in any investigational drug or device trial within 30 days prior to screening or concurrent participation in another research study that could complicate interpretation of the study findings.

3. Withdrawal/Termination criteria:

Subjects may discontinue the study at any time. The investigator may discontinue a subject at any time for subject safety or noncompliance. Subjects who are discontinued for safety will be referred to their primary care physician for follow-up.

The Investigator/Coordinator will complete a study exit form in the CRF for any subject who prematurely discontinues from the study. If discontinuation was the result of an AE, the AE also will be recorded in the CRF.

4. Allowable Medications/Nonpharmacological Therapies

The following medications and nonpharmacological therapies may be taken or used throughout the study:

- Aspirin for cardio-protection at a maximum stable dose provided the dose was stabilized over 3 months prior to study entry.
- Physical therapy/bracing for the knee joint if the program was initiated and consistent prior to study entry.
- Acetaminophen may be taken (up to 3000 mg per day) as rescue medication, if needed. Rescue medication is used only to treat worsening pain, whether or not that pain is associated with knee (e.g, may be used to treat headache, acute injury, etc.) and is not used for prophylaxis.
- Use of acetaminophen must be discontinued 48 hours prior to the procedure visit and each follow-up visit.

5. Restricted Medications/Nonpharmacological Therapies

Volunteers will be advised that participation in the study will require them to abstain from certain medications and therapies. The following medications and nonpharmacological therapies should not be taken or used beginning immediately upon enrollment (after signing informed consent) until subject reaches the end of the study:

- Oral non-steroidal anti-inflammatory drugs (unless on a chronic stable dose for ≥ 3 months prior to enrollment).
- Topical analgesics applied to the skin over the knee (e.g., NSAID's, capsaicin, lidocaine, heat patches).
- Orally administered systemic corticosteroids.
- Other Intra-articular injection into the knee joint.
- Centrally acting pain medications (e.g., pregabalin, gabapentin, duloxetine, milnacipran) (unless on a chronic stable dose for ≥ 3 months prior to enrollment).

E. Specific methods and techniques used throughout the study

Investigational Product

Zilretta kits will be received from Flexion Therapeutics and stored in a refrigerator between 2-8 degrees Celsius upon receipt. An 'Investigational Drug Accountability Record' will be used to record the product use for each subject. The kit label number, date of receipt, dates of dispense and preparation, and the date of destruction of the remaining product will be tracked and logged.

Treatment Procedure:

Zilretta (triamcinolone acetonide extended-release injectable suspension) is indicated as an intra-articular injection for the management of pain due to knee OA. To prepare the injectate, we will dilute 32 mg Zilretta in a 5 ml diluent for each knee, per manufacturer instructions. After application of sterile chlorhexidine and topical lidocaine (optional) for skin anesthesia, we will locate the superior recess of each knee joint, aspirate excess joint fluid and then inject the 5ml injectate into each knee joint capsule (bilateral injections).

Primary Outcome

OARSI recommended physical performance measures

OARSI (Osteoarthritis Research Society International) recommended physical performance measures¹ are a consensus-derived set that test physical function, which is complementary to patient-reported measures for

use in people diagnosed with knee osteoarthritis or following knee replacement. They are recommended for use prospectively as outcome measures in research, and also in clinical practice to make treatment decisions based on the results¹¹.

1. 30-second chair standing test

The 30-second chair standing test evaluates the maximum number of repetitions that a subject can stand from a seated position in a 30 second period¹. From the sitting position, the subject will stand up completely up so hips and knees are fully extended, then completely back in the seated position. This will be repeated for 30 seconds and we will record the total number of chair stands (up and down equals one stand). The tester will stand close to the side of the chair for safety and also ensure that the subject comes to a full standing and sitting position during the test.

The study coordinator or designee will enter the data collected into the CRF after completion of the test.

2. 40m fast-paced walking test

The 40-meter fast-paced walking test is a test that is timed over 4 x 10m (33 ft) paths for a total of 40 m (132 ft)¹. We will mark out a 10 m (33 ft) walkway with bright colored tape at each end. A cone will be placed approximately 2 meters before the start mark and 2 meters beyond the finish mark of the 10m walkway. Enough space will be left to turn safely around at each end.

A practice trial of 1-2 turns will be done before testing to help subjects to understand the procedure. We will begin timing subjects after giving the signal to start at the start line and stop the timer once the subject crosses back over the start line after completing the course. When the subject crosses the 10m mark, timing will be paused while the subject turns around the cone and then it will be resumed once they cross the 10m mark again. The same will be repeated for the following turns and timing will be stopped once the subject crosses the start line for the final time. The duration of one trial will be recorded to the nearest 100th of a second. Time of one test trial will be recorded and expressed as speed (m/s) by dividing distance (40m) by total time. Regular walking aid will be allowed and its use will be recorded.

For subjects in whom safety is of concern, the tester will follow slightly behind and off to one side of the subject, while taking care not to pace or impede them. If there is no excess concern for safety, the tester will follow well to the side so as to view the crossing at the 10m walkway at both ends. The study coordinator or designee will enter the data into the CRF.

3. Stair negotiation

Stair negotiation is also a common activity limitation and rehabilitation goal in people with symptomatic knee OA. We will time the subjects ascending and descending a flight of 9 stairs as quickly as they can accomplish in a safe manner. We will conduct the nine-step stair test in the staircase adjoining our research space (individual step height of 17 cm).

Timing will begin on the signal to start and terminate when the subject returns with both feet to the ground level. Total time to ascend and descend steps for 1 test trial will be recorded to the nearest 100th of a second.

Use of a handrail and walking aid will be permitted if required¹. The study coordinator or designee will enter the data into the CRF.

Secondary Outcome

Patient-reported physical function (KOOS-PS).

In addition to the performance-based primary outcome measures, KOOS-PS, a self-reported measure of mobility will be included.

KOOS-Physical Function (KOOS-PS) Short Form is a parsimonious measure of physical function derived from the KOOS¹². The KOOS-Physical Function Short Form also has good internal consistency and high

test-retest reliability.

A working group tasked with constructing a composite measure of OA severity sponsored by the Osteoarthritis Research Society International (OARSI) and Outcome Measures in Rheumatology (OMERACT) developed the KOOS-PS. Respondents are asked to indicate the degree of difficulty experienced in the last week due to a knee problem in 7 tasks: Rising from Bed, Putting on socks/stockings, Rising from sitting, Bending to the floor, Twisting/pivoting on the injured knee, Kneeling, and Squatting. Responses are measured on a Likert scale ranging from 'None' to 'Extreme'.

Tertiary Outcomes

KOOS QoL

KOOS-QoL is a self-reported measure¹³ (4 questions) of quality of life, which is part of the five patient-relevant subscales of KOOS. A Likert scale is used and all four questions have five possible answer options scored from 0 (No Problems) to 4 (Extreme Problems). Each of the five scores is calculated as the sum of the items included. Scores are transformed to a 0-100 scale, with zero representing extreme knee problems and 100 representing no knee problems as is common in orthopedic assessment scales and generic measures. Scores between 0 and 100 represent the percentage of total possible score achieved.

Numerical Rating Scale (NRS) for Pain

The Numeric Rating Scale for Pain (NRS for Pain) is a measure of pain intensity. The investigator or designee will verbally introduce the 11-point scale to the research subject to rate pain in each knee. The investigator or designee will ask the following questions,

- “On a scale of 0 to 10, with 0 being no pain at all and 10 being the worst pain imaginable, how would you rate your knee pain IN THE PAST 7 DAYS?”

The subject will complete the NRS for Pain worksheet after receiving instructions from the study coordinator. The NRS for Pain will be completed by the subject at baseline evaluation and at each follow-up visit (6,12 and 24 weeks). The study coordinator or designee will enter the data into the CRF.

The table below details the schedule of study assessments and procedures, for each visit.

Assessment	Visit 1 Screening	Visit 2 Day 1- Zilretta Treatment [‡]	Visit 3 6-Week Follow-up	Visit 4 12-Week Follow-up	Visit 5 24-Week Follow-up
Informed Consent	X				
Eligibility	X	X [‡]			
Medical history	X	X [‡]			
Radiograph (if not previously done)	X				
Concomitant medications	X	X [‡]	X	X	X
Prior/Concurrent Therapy	X				
Study Treatment		X			
BMI Assessment	X				
Physical Exam		X	X	X	X
KOOS-PS & QoL Questionnaire		X	X	X	X
NRS for Pain	X	X [‡]	X	X	X
Physical Performance Measures			X	X	X
AE/SAE Assessment		X	X	X	X

*Each visit must be within ± 5 days of the scheduled visit; [‡] may be combined with screening visit.

F. Risk/benefit assessment

The reference safety information for Zilretta for this study is the Zilretta USPI.

1. Physical risk:

Zilretta (triamcinolone acetonide extended-release injectable suspension) is indicated as an intra-articular injection for the management of pain due to knee OA. The most commonly reported adverse reactions (incidence $\geq 1\%$) in clinical studies included sinusitis (2%), cough (2%), contusions (2%) and joint swelling (3%). For additional details, please see Package Insert (<http://www.zilrettalabel.com/PI.pdf>). The website for Zilretta additionally lists: joint pain, headache, back pain, sore throat and runny nose, and bruising as common side effects of receiving a Zilretta injection.

The following is a list of other adverse events that can occur following injection of corticosteroids, although not reported following Zilretta.

- **Hypersensitivity Reactions:** Rare instances of anaphylaxis, including serious cases, have occurred in patients with hypersensitivity to corticosteroids. Serious cases of anaphylaxis, including death, have been reported in individuals receiving triamcinolone acetonide injection, regardless of the route of administration.
- **Joint Damage:** Intra-articular administration may result in damage to joint tissues.
- **Increased Risk of Infections:** Infection with any pathogen in any location of the body may be

associated with corticosteroids. Corticosteroids may increase the susceptibility to new infection and decrease resistance and the ability to localize infection. A marked increase in pain accompanied by local swelling, restriction of joint motion, fever, and malaise are suggestive of septic arthritis.

- **Alterations in Endocrine Function:** Corticosteroids can produce reversible hypothalamic-pituitary-adrenal axis suppression, with potential for adrenal insufficiency after withdrawal of treatment, which may persist for months.
 - **Cardiovascular and Renal Effects:** Corticosteroids can cause blood pressure elevation, salt, and water retention, and an increase potassium excretion.
 - **Increased Intraocular Pressure:** Corticosteroid use may be associated with increased intraocular pressure.

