Data regarding subject's demographic, knee radiographs, OARSI recommended physical performance measures, and KOOS subscale responses and NRS pain data will be obtained directly from subjects. All data will be coded with no information that could identify a subject. A master list with patient information and assigned study ID's will be stored in a password-protected file available only to the Principal Investigator and the Research Coordinator. Analyses will be performed on coded files. Physical files (e.g. questionnaires) will be stored in locked file cabinets in the office of the Principal Investigator.

E. Quality Assurance / Monitoring

Study staff will have proper qualifications for data entry and will receive training in data entry procedures to ensure data entered is of highest quality. Data will be entered by researchers into two separate databases developed for this study. Each database will contain the same collection points and then be reconciled to clean the data for analysis and outcome reports to the Principal Investigator. Data will be backed-up daily.

V. Data Analysis and Reporting

A. Statistical and Data Analysis:

The primary analysis will regard the change in the 3 OARSI-recommended physical performance measures between baseline and 12 weeks following injections. The three pre/post change scores will be assessed with one-sample t-test for matched pairs, using an alpha level of (.05/3) to determine statistical significant change.

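### The 80% power claimed for 60 subjects holds only if the primary tests are one-sided, which the plan does not say; two-sided power is 71.5% at 60 and 79.3% at 70

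*Combined protocol and SAP*

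**What the plan says.** Section II.C sets the significance level for the three primary performance tests: "The overall type I error rate will be controlled with an alpha level of 0.0167 to account for three comparisons". It then gives the assumed effect, stating that "the effect size for this minimal detectable change is 0.392", and concludes that "with an adjusted alpha of 0.0167 and 80% power, a sample size of 60 would be required". On recruitment it adds: "To accommodate up to 14% dropout, we plan to recruit 70 subjects".

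Section V.A defines the primary analysis of the three change scores from baseline to 12 weeks as a "one-sample t-test for matched pairs, using an alpha level of (.05/3) to determine statistical significant change".

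Neither section says whether the tests are one-sided or two-sided. The aims are worded in one direction. Section I.A expects that patients "will experience significant improvement in physical performance, physical function and quality of life", Primary Hypothesis 1 is that treatment "results in improved physical performance detectable at" the three follow-up times, and II.A sets out to "evaluate the efficacy of Zilretta for improving physical performance". Section V.B also expects improvement. None of these statements declares a one-sided test.

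**The concern.** The sample size claim depends on a choice that the plan does not record. If the three t-tests are run two-sided, as is usual when no side is given, 60 evaluable subjects do not give 80% power for an effect of 0.392, and nor do all 70.

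The choice can also decide the primary result, because some observed changes are significant under one reading and not under the other. The study is open-label with a single arm, and section V.A plans database soft-locks after the 6- and 12-week time points. A side left open until then could be chosen after follow-up data have been seen. Nothing in the document suggests that anyone intends this, but nothing prevents it.

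**Working it through.** **Inputs.** Standardised mean change d = 0.392, power 80%, n = 60, 70 recruited and 14% dropout come from II.C. The test (one-sample t on change scores) and alpha = .05/3 per test come from V.A; II.C rounds alpha to 0.0167. The inputs behind 0.392 are not given, so it is taken as an assumed mean change divided by the SD of change.

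**Formula.** Under the alternative, the t statistic is noncentral t with n − 1 degrees of freedom and noncentrality d√n. At n = 60 the noncentrality is 0.392 × √60 = 3.036. One-sided power is the probability of exceeding the upper alpha point. Two-sided power is the probability of falling beyond either alpha/2 point.

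**The plan's own figure.** One-sided at .05/3, power is 79.5% at n = 59 and 80.2% at n = 60, so 60 is the smallest n that reaches 80%. The dropout step is also right: 60/0.86 = 69.8, hence 70.

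**Both readings, per test:**

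| Evaluable | One-sided power | Two-sided power | Effect detectable two-sided with 80% power |
|---|---|---|---|
| 60 | 80.2% | 71.5% | 0.428 |
| 65 | 83.5% | 75.7% | 0.411 |
| 70 | 86.4% | 79.3% | 0.395 |

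The smallest two-sided n for 80% is 72 (71 at the rounded 0.0167). At 14% dropout, 72/0.86 = 83.7, or 84 recruited (71/0.86 = 82.6, or 83).

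**Other routes to 60.** The normal approximation n = ((z_alpha + z_power)/d)² at 0.0167 gives 57.4 (58) one-sided and 68.1 (69) two-sided. The exact t-test gives 54 at two-sided 0.05 and 65 at two-sided 0.025. Two-sample formulas give 115 or 137 per arm. Of the versions tried, only the exact one-sided paired t-test gives 60. Rounding of 0.392 (0.3915 to 0.3925) leaves the one-sided n at 60 and the two-sided n at 71 to 72.

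**Where the conclusion changes.** At n = 60 the critical t is 2.179 one-sided and 2.464 two-sided. Dividing by √60 = 7.746 gives observed changes of 0.281 and 0.318 SD. A result between these is significant only one-sided.

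**Dependence on the true effect, n = 60 (one-sided against two-sided power).** 56.0% against 45.0% at 0.3; 80.2% against 71.5% at 0.392; 95.3% against 91.7% at 0.5; 99.2% against 98.4% at 0.6.

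**The three tests together.** Simulation of 40,000 trials per scenario, two-sided, n = 60, all three effects 0.392, with correlation between measures assumed to be 0.3 to 0.7: at least one test succeeds in 87–94% of trials and all three in 44–55%.

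**Holm in place of Bonferroni.** Same simulation, two-sided, per-test power with all three effects 0.392: from about 72% to 79–80% at 60, from 76% to 83–84% at 65, and from 79% to 85–87% at 70. At n = 60 it is about 75% if two effects are 0.392 and essentially unchanged if only one is. Holm's familywise error at n = 60 was at most 0.046 in every configuration tried.

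**The case against.** The best defence is that nothing was miscalculated. Sixty is exactly the one-sided answer and every stated aim is improvement, so the simplest reading is a one-sided calculation with the word left out. The two-sided default is a convention from outside the document. This largely stands: the defect is an undeclared side, not a demonstrated arithmetic error. But a directional hypothesis does not declare a one-sided test, and V.A speaks only of change. The direction is not even settled for each measure. Sections I.B and IV.A call the walking result a time, while II.E converts it to a speed; they also call the chair stand a time, while II.E records a count.

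Second, the harm is conditional and modest. It arises only if the tests are two-sided, is under 1 point with full retention, and shrinks if the true effect exceeds 0.392, which II.C treats as a minimum. The study is also titled a pilot. All of this is fair and limits the severity. Still, the plan budgets for 14% dropout, and at that level the gap is about 9 points.

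Third, splitting alpha three ways fits a rule under which any one success counts, and then two-sided power at 60 is 87–94%, above 80%. That is a reasonable inference, although the plan does not state the rule. The 80% in II.C reproduces as a per-test figure, so per-test power is the right comparison.

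Fourth, Bonferroni is valid as planned, so Holm corrects no error. That is correct; it is an optional improvement.

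**Conclusion.** The concern holds. The claim of 80% power with 60 subjects is true one-sided (80.2%) and untrue two-sided (71.5%), and the available text declares neither. Read two-sided, the stated power is not reached at any dropout level the plan allows for: the shortfall is about 9 points at 14% dropout, about 4 points with 65 evaluable (7% dropout) and under 1 point with none. These are per-test figures at alpha .05/3. They take 0.392 as the mean change divided by the SD of change, and they use the t-test the plan names. The normal approximation would give 74.0% at 60 and 81.2% at 70, but it is not the planned analysis. The matter should be fixed before the data are seen; it does not call the design into question.

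**What to change.** State the side in both II.C and V.A, before the 12-week data are seen and preferably before the 6-week soft-lock.

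- *If two-sided.* II.C could read: Each primary t-test is two-sided at .05/3. With 60 evaluable subjects, per-test power is about 72% for a mean change / SD of change of 0.392 and 80% for 0.43 (79% for 0.392 if all 70 are evaluable). V.A should then specify two-sided one-sample t-tests on the change scores.
- *If one-sided.* Declare it in both sections, give the direction of benefit for each measure on the scale analysed, and keep n = 60. This route allows up to 3 × .05/3 = 5% familywise error for falsely claiming benefit, against 3 × .05/6 = 2.5% in that direction under two-sided tests. The choice should be made with that in view.

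In either case, label 0.392 as an assumed standardised mean change.

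An optional improvement is to replace Bonferroni with Holm at overall 0.05: smallest p-value against .05/3, next against .05/2, largest against .05, stopping at the first non-significant result. It keeps the 0.05 familywise limit and never rejects fewer hypotheses.

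The cost is wording only, with no added subjects. If the tests are two-sided, the stated power becomes less favourable; restoring 80% under Bonferroni at 14% dropout would instead mean recruiting 83 to 84. Holm has no simple matching simultaneous confidence intervals, and its gain depends on at least two of the three measures responding.
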